2 STUDY OBJECTIVES AND DESIGN

2.1 Objectives

Primary Objective

The primary objective is a composite endpoint with four elements:

- To demonstrate that the geometric mean RVNA concentration for SYN023 recipients is superior to the geometric mean RVNA concentration for HRIG recipients on Study Day 8 AND
- To demonstrate that the Study Day 99 geometric mean RVNA concentration for SYN023 recipients is not inferior to the geometric mean RVNA concentration for HRIG recipients AND
- To demonstrate that the percentage of subjects with RVNA concentration ≥ 0.5 IU/mL on Study Day 99 in SYN023 recipients is not inferior to the percentage of recipients with RVNA concentration ≥ 0.5 IU/mL for HRIG AND
- There are no probable or confirmed cases of rabies in SYN023 recipients.

Secondary Objective(s)

- To demonstrate that the geometric mean RVNA concentration for SYN023 is superior to the geometric mean RVNA concentration for HRIG on Study Day 4
- To demonstrate that the geometric mean RVNA AUEC₁₋₁₅ for SYN023 is superior to the geometric mean RVNA AUEC₁₋₁₅ for HRIG
- To describe the ratio of the geometric mean concentrations of RVNA at each time point in SYN023 recipients divided by the geometric mean concentrations of RVNA in HRIG recipients for LRG and NRG in the per-protocol and as-treated populations.
- To describe the percentage of RVNA concentration ≥ 0.5 IU/mL at each time point for SYN023 and HRIG recipients for LRG and NRG in the per-protocol and as-treated populations.
- To describe the pharmacokinetics of SYN023 using non-compartmental analysis. V_d, C_{max}, T_{max}, AUC_{1-t}, AUC_{1-inf}, t_{1/2}, Cl, and λ_z will be calculated when possible in the LRG and NRG protocol and as treated populations.
- To evaluate presence and effects of anti-SYN023 antibodies (anti-CTB011, anti-CTB012)
- To evaluate the safety of SYN023 compared to HyperRab® S/D
- To describe any effect of increasing BMI on SYN023 and RVNA concentrations.

2.2 Design

This is a Phase 2b, double blinded, randomized study of SYN023 compared to HyperRab® S/D (a licensed HRIG) for PEP of patients who have been confirmed to have met all inclusion/exclusion criteria for their treatment group. The desired indication is the prevention of rabies as part of PEP. The trial will be conducted in least two countries where rabies occurs. The trial will enroll sequentially two different risk substrata of WHO Category 3 rabies exposure.

2.2.1 Low Risk Group (LRG)

The Low Risk Group (LRG) is composed of subjects who meet the modified WHO Category 3 protocol exposure criteria (Table 2.2-1 below and Sections 3.9.4 and 3.9.5). Inclusion is limited to bites to the foot, ankle, leg or trunk and licks to broken skin, scratches with, or to broken skin, unprotected bat exposure or mucous membrane contamination by saliva or neural tissue. These exposures represent a lower rabies risk exposure within WHO Categories 3. Bites to the head, neck or genitalia are excluded from LRG Initial Enrollment and LRG General Enrollment (Section 2.2.2 to Section 2.2.4). The purpose of the LRG is to obtain early safety, pharmacodynamic and pharmacokinetic information from field sites. Since it does not have the same rabies risk as the NRG it, will be analyzed separately for clinical rabies.

Table 2.2-1 Exposure Characteristics of the Low Risk Group and Normal Risk Group

Exposure Type	LRG	NRG
Head and neck bite	-	+
Genitalia bite	-	+
Arms bite	-	+
Hands bite	-	+
Trunk bite	+	+
Legs bite	+	+
Ankles bite	+	+
Foot bite	+	+
Non-bite lick	+	+
Non-bite scratch	+	+
Non-bite bat contact	+	+
Non-bite mucous membrane	+	+

2.2.2 Initial Enrollment in the LRG (20 Subjects)

Safety and RVNA data through Study Day 29 from the initial 20 subjects of the LRG will be reviewed by the DSMB to confirm safety and the achievement of adequate RVNA levels ≥ 0.5 IU/mL on Study Day 15 and 29 from standard, wound management, Study Drug administration and rabies vaccination before LRG general enrollment is permitted. Subjects excluded for cause by the Per-protocol Adjudication Board (Section 3.2.8) will not be included in the RVNA per-protocol analysis but will be included in as-treated population. The initial 20 subjects in the LRG will be randomized on a 3:1 (SYN023 to HRIG) ratio. The size of the initial LRG enrollment is arbitrary. The initial LRG enrollment is not part of the sample size calculations for the primary objective.

2.2.3 Advancement from Initial Enrollment LRG to General Enrollment LRG

The DSMB will permit enrollment of the General LRG Enrollment group if safety from the as-treated population and RVNA pharmacodynamic data from the per protocol population Study Days 8-29 from the initial LRG enrollment are found to be satisfactory by the DSMB (Section 5.1.5.2).

2.2.4 General Enrollment LRG

The LRG general enrollment of an additional 60 subjects will consist of low risk WHO Category 3 exposures (Table 2.2-1, Section 3.9.4 and 3.9.5). Subjects General Enrollment LRG will be allocated with a 1:1 randomization to either SYN023 or HRIG treatment arms. Bites to the head, neck or genitalia are not included in the LRG.

2.2.5 Advancement from LRG General Enrollment to the Normal Risk Group (NRG)

If Study Day 99 efficacy (RVNA) and safety LRG data from the initial and general enrollment have been judged to be adequate by the DSMB and there are no cases of rabies in SYN023 recipients by Study Day 183 then randomization into the NRG will be permitted (Section 5.1.5.3). It is presumed that a case of clinical rabies in the study population would become known to the DSMB promptly. Clinical rabies follow-up of the LRG will be made available to the DSMB through 6+ months on all patients for consideration of NRG commencement. The 12 months of LRG follow-up will not have ended when NRG enrollment starts.

2.2.6 The Normal Risk Group (NRG)

The NRG will consist of all WHO Category 3 exposure (Table 2.2-1, Sections 3.9.4 and 3.9.5). The NRG includes all rabies risks. It is powered to evaluate the primary and some secondary study objectives and to contribute to the pharmacokinetic and pharmacokinetic description of SYN023.

2.2.7 Enrollment of the NRG

Subjects will be allocated with a 1:1 randomization to either SYN023 or HRIG treatment arms. Within the NRG group bites to the head, neck or genitalia that have the highest rabies risk will be stratified for each treatment arm in a 1:1 ratio. The DSMB will review the progress of pharmacodynamic and safety data during the NRG study period to avoid unnecessary risk or expense (Section 5.1.5.4).

2.3 Study Trial Size

Data from an initial subgroup of 20 subjects will be evaluated by the DSMB to ensure pharmacodynamic activity before the remainder of the LRG is enrolled. The size of this group was determined by non-statistical reasons (Table 2.3-1).

Safety and pharmacodynamic data from the entire LRG will be reviewed by the DSMB to ensure safety and pharmacodynamic adequacy. The size of the LRG is 80 subjects. Up to 45 LRG subjects will have received SYN023. This number was judged adequate to give a preliminary assessment of Study Drug performance in the LRG.

Three hundred and twenty patients are required in the per-protocol population to satisfy the efficacy elements of the AUEC-1-15 secondary endpoint. Synermore anticipates approximately 15% (48 patients) of loss to follow-up and exclusions resulting in a total NRG size of 368. Since PEP should not be delayed and some inclusion/exclusion criteria may not be known at the time of randomization some subjects may be excluded (but not replaced) from the per-protocol population by the Per-Protocol Adjudication Board if they are later discovered to have met an exclusion criterion.

Randomization will be adjusted by the randomization center such that patients are proportionately distributed between the trial sites and patients with wounds of the head, neck or genitalia are stratified approximately equally into the treatment groups.

Table 2.3-1 Enrollment by Risk Group and Treatment

Group	Enrollment	Treatment	Rabies Vaccination	Number of subjects
LRG	initial	HRIG 20 IU/kg	Day 1,4,8,15,29	5
LRG	initial	SYN023 0.3 mg/kg	Day 1,4,8,15,29	15
LRG	general	HRIG 20 IU/kg	Day 1,4,8,15,29	30
LRG	general	SYN023 0.3 mg/kg	Day 1,4,8,15,29	30
NRG	general	HRIG 20 IU/kg	Day 1,4,8,15,29	184
NRG	general	SYN023 0.3 mg/kg	Day 1,4,8,15,29	184
Total required for initial LRG enrollment				20
Total required for general LRG enrollment				60
Total required for NRG enrollment				368
Total maximum enrollment				448

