Three hundred and twenty patients are required in the per-protocol population to satisfy the efficacy elements of the AUEC-1-15 secondary endpoint. Synermore anticipates approximately 15% (48 patients) of loss to follow-up and exclusions resulting in a total NRG size of 368. Since PEP should not be delayed and some inclusion/exclusion criteria may not be known at the time of randomization some subjects may be excluded (but not replaced) from the per-protocol population by the Per-Protocol Adjudication Board if they are later discovered to have met an exclusion criterion.

Randomization will be adjusted by the randomization center such that patients are proportionately distributed between the trial sites and patients with wounds of the head, neck or genitalia are stratified approximately equally into the treatment groups.

Table 2.3-1 Enrollment by Risk Group and Treatment

Group	Enrollment	Dosage	Rabies Vaccination	Number of subjects
LRG	initial	HRIG 20 IU/kg	Day 1,4,8,15,29	5
LRG	initial	SYN023 0.3 mg/kg	Day 1,4,8,15,29	15
LRG	general	HRIG 20 IU/kg	Day 1,4,8,15,29	30
LRG	general	SYN023 0.3 mg/kg	Day 1,4,8,15,29	30
NRG	general	HRIG 20 IU/kg	Day 1,4,8,15,29	184
NRG	general	SYN023 0.3 mg/kg	Day 1,4,8,15,29	184
Total required for initial LRG enrollment				20
Total required for general LRG enrollment				60
Total required for NRG efficacy element				368
Total maximum enrollment				448

Study Duration

Subjects will be followed for 365 days post receipt of Study Drug unless withdrawn from the trial. It is important to have follow-up information on all study enrollees for the full duration of the study. Every effort should be made to remain in contact with study subjects in at least six-

week intervals to establish if the subject is in good health and to inquire about planned relocations. If health problems have occurred a verbal or written account of the duration and character of the difficulties should be obtained. This is specially important in the last six months of the study when clinic visits are less frequent.

Study Populations

Failure to meet inclusion/exclusion criteria at initial screening

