2.7 Non-Replacement of Randomized Patients

Subjects will not be replaced after randomization. They may be excluded from the per-protocol population

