7.8.4 Superiority of Secondary endpoint AUEC1-15

$H_0: \emptyset \leq \emptyset_L$ where $\emptyset_L > 1$

Where, $\emptyset = \frac{GM_{SYN023}}{GM_{HRIG}}$; GM is the geometric mean.

The alternative hypothesis for superiority is expressed as: $H_1: \emptyset > \emptyset_L$.

The calculation of the sample size requires defining the range of the true mean ratio [AUEC₁₋₁₅ (SYN023/RIG): 147.55%, 90% CI: 115.10%, 189.14%], margin of superiority [10%], power [80%], coefficient of variation [CV: 108.78%] and alpha [0.025]. The calculation is done in PASS 15 software for the defined range of the true mean ratio and the results are presented for only those values for which the sample size is considered feasible.

A true AUEC₁₋₅ geometric mean ratio of SYN023/ HRIG of at least 1.45 and 80% power would therefore require a sample size of 320 with equal number of subjects in two groups for detecting the superiority with 10% of margin. Based on a true geometric mean ratio of at least 1.45, a total sample size of 320. A higher total sample of 368 allows for drop-outs and lost to follow up.

7.8.5 Absence of Rabies:

Synermore estimates that any PEP failure rabies cases occurring in the trial will be more likely due to a failure of clinical management or failure to follow protocol specified procedures or less likely intrinsic resistance to post-exposure prophylaxis. Synermore estimates this possibility of rabies at approximately 0.1% to 0.01%. This means there is a small chance of a single case of confirmed rabies occurs in the 184 subjects in the SYN023 NRG group. If one case of PEP failure occurs the point incidence of PEP failure will be 0.6% and the 95% confidence interval will extend from 0% to 2.0%. A 0.6% failure rate is high enough to be evidence of lack of efficacy and thus a failure of the primary objective.

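### The 15% attrition allowance was added to 320, not taken from 368, so a 15% loss leaves about 313 evaluable subjects instead of the 320 required

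*Protocol*

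**What the plan says.** Protocol section 2.3 (Study Trial Size), repeated in the Study Abstract, takes its target from a secondary endpoint: "Three hundred and twenty patients are required in the per-protocol population to satisfy the efficacy elements of the AUEC-1-15 secondary endpoint". It then adds the allowance: "Synermore anticipates approximately 15% (48 patients) of loss to follow-up and exclusions resulting in a total NRG size of 368". Table 2.3-1 splits the 368 as 184 per arm.

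Protocol section 7.8.4 gives the source of the 320. A true AUEC1-15 geometric mean ratio "of at least 1.45 and 80% power would therefore require a sample size of 320 with equal number of subjects in two groups". It closes without a percentage: "A higher total sample of 368 allows for drop-outs and lost to follow up". That sentence is context and does not itself repeat the error.

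Protocol section 2.7 rules out topping up: "Subjects will not be replaced after randomization".

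SAP section 4.1 keeps both 320 and 368 but gives no attrition rate, describing the allowance only as reasonable. It refers the reader to protocol section 7.8 for detail.

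**The concern.** An attrition rate is normally a share of the subjects who enter, because they are the ones who can be lost or excluded. The protocol's 48 matches 15% only when it is divided by the number required at the end. Divided by the number enrolled it is 13.0%. The three stated figures (320 required, 15% lost, 368 enrolled) therefore cannot all be true.

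The base matters more than usual in this trial. The per-protocol population is primary, and SAP section 8.2 runs the AUEC1-15 test on it in the NRG. Exclusions can come from several sources: Day 1 RVNA of 0.1 IU or more (the protocol's rationale expects evidence of unrecalled vaccination in 2% to 5% of subjects), delay beyond 54 hours, incomplete vaccination, and untreated exposure sites. With no replacement, a shortfall cannot be made good later. At stake are the evaluable number and the 80% power stated for AUEC1-15.

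**Working it through.** **Inputs.** Required per-protocol total 320, loss 15% or 48 patients, enrolled 368 (protocol 2.3). No replacement (2.7). Allocation 1:1 (2.2.7). For AUEC1-15: true ratio 1.45, superiority margin 10% (bound 1.10), CV 108.78%, alpha 0.025, power 80% (7.8.4). Alpha is read as one-sided because the alternative hypothesis is one-directional.

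**1. Reproduce the plan's enrolment.**
- 320 × 0.15 = 48
- 320 × 1.15 = 368

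Both match exactly, so the allowance was added as n × (1 + d).

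**2. Apply 15% to those enrolled.**
- Lost: 368 × 0.15 = 55.2, about 55 rather than 48
- Remaining: 368 × 0.85 = 312.8, about 313 (184 × 0.85 = 156.4 per arm)
- Shortfall: 320 − 313 = 7
- Attrition at which 368 leaves exactly 320: 48/368 = 13.0%

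**3. Enrolment needed for 320 after 15% loss**, using n/(1 − d):
- 320/0.85 = 376.5, so 377, or 378 (189 per arm) for equal arms
- That is 9 or 10 more than 368

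**4. Check the base figure of 320.**
- Log-scale SD = √ln(1 + 1.0878²) = 0.8837
- Effect = ln(1.45/1.10) = 0.2763
- n per arm = 2 × [0.8837 × (1.960 + 0.842)/0.2763]² = 160.6, so 161 per arm, 322 in total
- A t-based calculation gives 162 per arm, 324 in total

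The 320 is thus reproduced to within a few subjects. Reading alpha as two-sided 0.025 gives 390, and one-sided 0.05 gives 254. Neither matches, which supports the one-sided 0.025 reading.

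**5. AUEC1-15 power under the same inputs.**

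| Evaluable total | t-test | Normal approximation |
|---|---|---|
| 320 | 79.6% | 79.8% |
| 313 | 78.7% | 79.0% |

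The allowance error costs 0.9 of a percentage point. The rest of the gap to 80% comes from 320 itself lying slightly under the 322 to 324 found in step 4.

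**The case against.** The protocol never says 15% of whom. It writes approximately, and it gives a count: 368 − 48 = 320 closes exactly. On that reading the subject counts agree and only a rounded percentage is loose; if 48 are lost, 320 remain. This is fair, but it does not rescue the sentence. If 48 is right, the rate against enrolment is 13%; if 15% is right, the count is 55. One of the two needs correcting.

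The stronger objections concern consequence, and most of them stand:

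- AUEC1-15 is secondary. The largest requirement for a primary element in Table 7.8-1 is 138 in total, far below 313.
- Section 7.8.4 quotes an estimated ratio of 147.55% and powers on 1.45. At a true ratio of 1.4755, power at 313 is 83.4%.
- SAP section 8.2 states no 10% margin for AUEC1-15. If the test is against a ratio of 1, as SAP section 8.1.1.1 does for Study Day 8, power at 313 and a ratio of 1.45 is about 96%. The SAP does not spell out that null hypothesis, so this is conditional.
- AUEC1-15 needs samples only to Study Day 15, so later loss to follow-up need not remove data. Against this, protocol section 1.6 excludes from the per-protocol population subjects who leave the trial or whose status is unknown, so later losses may still count.

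These points limit the damage. They do not make 48 equal to 15% of 368.

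**Conclusion.** The point holds as a minor arithmetic error. The allowance was computed on the required number, so 368 delivers 320 evaluable subjects only if attrition is no more than 13.0%. At the stated 15%, about 313 remain, 7 too few, and AUEC1-15 power is 78.7% instead of the stated 80%. Under the protocol's inputs there is no reserve to absorb this, since power is already 79.6% at 320.

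The conclusion rests on reading attrition as a share of those enrolled, on every loss or exclusion removing a subject from the AUEC1-15 analysis, and on the section 7.8.4 inputs with one-sided alpha 0.025. A larger true ratio or a null ratio of 1 would give more power. The primary elements are not put at risk on the plan's own figures.

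**What to change.** Keep 368 and correct the text in protocol section 2.3 and the Study Abstract. State that 368 enrolled allows 13% attrition (48 of 368) for 320 evaluable. Add that at 15% attrition about 313 are evaluable and AUEC1-15 power is about 79% with the 10% margin, a ratio of 1.45 and a CV of 108.78%. Give the same rate in SAP section 4.1 in place of the unquantified allowance.

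The cost is wording and a slightly less favourable power figure, with no added subjects and no design change. If the sponsor wants 320 evaluable at a true 15% loss, enrolment would have to rise to 378 (189 per arm), 10 more subjects. A gain of about one power point on a secondary endpoint hardly calls for that.

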2.4 Study Duration and Follow-up

Subjects will be followed for 365 days post receipt of Study Drug unless withdrawn from the trial. It is important to have follow-up information on all study enrollees for the full duration of the study. Every effort should be made to remain in contact with study subjects in at least six-week intervals to establish if the subject is in good health and to inquire about planned relocations. If health problems have occurred a verbal or written account of the duration and character of the difficulties should be obtained. This is specially important in the last six months of the study when clinic visits are less frequent.

2.5 Study Populations

2.5.1 Failure to Meet Inclusion/exclusion Criteria at Initial Screening

Screening includes informed consent, satisfaction of inclusion criteria and an initial survey of exclusion criteria. Rabies exposed subjects that are known to fail inclusion criteria at initial screening or any immediately evaluable exclusion criteria will not be randomized into the study. They will be treated outside of the study protocol with the national standard of care for PEP. The minimum PEP standard will include ERIG or HRIG and rabies vaccination according to the national recommendations. Not all exclusion criteria need to be known at the time of randomization but those that are known will determine enrollment.

2.5.2 As-Treated Population

All subjects who are randomized and receive Study Drug are included in the “as-treated” population.

2.5.3 LRG Per-Protocol Population

Since PEP of rabies is urgent and should not be delayed, randomization and prophylaxis will begin after a screening event that includes informed consent and survey of inclusion criteria (including urine pregnancy test results) before some exclusion criteria have been confirmed. WHO Category 3 exposure victims that meet all initially knowable inclusion/exclusion criteria (Section 3.2.3 – 3.2.5) will be randomized receive wound treatment, receive Study Drug and begin a regimen of rabies vaccination.

2.5.4 NRG Per-Protocol Population

Since PEP of rabies is urgent and should not be delayed, randomization and prophylaxis will begin after a screening event that includes informed consent and survey of inclusion criteria (including urine pregnancy test) before some exclusion criteria have been confirmed. WHO Category 3 exposure victims that meet all initially knowable inclusion/exclusion criteria will be randomized receive Study Drug and begin a regimen of rabies vaccination.

2.6 Randomization

2.6.1 LRG Initial Enrollment Randomization

Subjects in the initial enrollment group will be randomized on a 3:1 basis to treatment with SYN023 or HRIG. Eligibility for the LRG subjects is described in Section 2.2.1. The group as described in Table 2.3.1 is randomized in a 3:1 ratio. Subjects in the initial LRG may be excluded from LRG the per-protocol population but they will not be replaced.

2.6.2 LRG General Enrollment and NRG Randomization

Subjects in the general enrollment of LRG and NRG will be randomized on a 1:1 basis within each group to treatment with SYN023 or HRIG. Subjects will be allocated to treatment sites to approximate the ratio in Table 2.3-1. Within NRG enrollment subjects with head or neck bites or bites to genitalia will be stratified on a 1:1 basis into SYN023 or HRIG treatment groups.

Study sites wishing to randomize a subject will contact the study randomization center either telephonically or by electronic means. The study center will determine the randomization allocation and return the randomization assignment in written communication to the study site.

2.7 Non-Replacement of Randomized Patients

Subjects will not be replaced after randomization. They may be excluded from the per-protocol population

2.8 Adjustments to Randomization

Allocation of randomization among sites will be adjusted to accommodate stratification of head, neck or genitalia bites or site enrollment imbalances.

3 STUDY PROCEDURES

3.1 Schedule of Subject Evaluations

A Summary Schedule of Evaluations depicting all visit-specific procedures is provided in Table 3-1. A more detailed description of the tasks and evaluations by Study Day is supplied in the Appendix. A table of phlebotomy volumes by visit may be found in Appendix C.

Table 3-1 Summary Schedule of Subject Evaluations LRG Group

Study Visit Day →	1	4	8	15	29	43	71	99	127	155	183	274	365
Visit window (days)	0	0	0	0	2	4	7	7	7	7	14	14	14
Written informed consent	X												
Eligibility criteria verification	X												
Medical history	X												
Physical examination	X												
ECG	X												
Urine βHCG (all females)	X												
Hepatitis B, C ^a	4												
HIV ^a	5												5
CBC, platelets ^a	2	2		2		2							
Urinalysis ^a	X												
Serum chemistry ^{a, c}	4	4		4		4							
PT(INR), PTT ^a	2					2							
Bite wound washing	X												
Vital signs	X	X	X										
Interval history		X	X	X	X	X	X	X	X	X	X	X	X
Focused physical examination		X	X	X	X	X	X	X	X	X	X	X	X
Wound photographs	X												
Randomization	X												
Study Drug Wound Injection	X												
Rabies Vaccination	X	X	X	X	X								
Serum RVNA	10 ^a	10 ^b	10 ^b	10 ^b	10 ^b	10	10	10	10	10	10	10	10
Confirmation visit	X	X	X										
Anti-SYN023 serum assay	5 ^a			5	5			5					
SYN023 concentration	5 ^a	5 ^b	5 ^b	5 ^b	5 ^b	5		5					
Adverse events (incl. con. Meds.)	X	X	X	X	X	X							
Solicited adverse events	X	X	X										
Serious adverse events (incl. con. Meds.)	X	X	X	X	X	X	X	X	X	X	X	X	X
Site of injection examination	X	X	X	X	X								
Per visit phlebotomy volume	37	21	15	26	20	23	10	20	10	10	10	10	15
Cumulative phlebotomy volume	37	58	73	99	119	142	152	172	182	192	202	212	227

- a. Study Day 1 samples must be obtained before Study Drug administration
- b. Samples must be obtained before vaccination.
- c. Serum chemistries are total bilirubin, AST, ALT, ALP, creatinine, blood urea nitrogen, sodium, potassium, chloride, bicarbonate, calcium.
- d. Numbers in lab specimen rows indicate **approximate** blood volume in mL.

Table 3-2 Summary Schedule of Subject Evaluations NRG Group

Study Visit Day →	1	4	8	15	29	43	71	99	127	155	183	274	365
Visit window (days)	0	0	0	0	2	4	7	7	7	7	14	14	14
Written informed consent	X												
Eligibility criteria verification	X												
Medical history	X												
Physical examination	X												
ECG	X												
Urine βHCG (all females)	X												
Hepatitis B, C ^a	4												
HIV ^a	5											5	
CBC, platelets ^a	2	2		2		2							
Urinalysis ^a	X												
Serum chemistry ^{a, c}	4	4		4		4							
PT(INR), PTT ^a	2					2							
Bite wound washing	X												
Vital signs	X	X	X										
Interval history		X	X	X	X	X	X	X	X	X	X	X	X
Focused physical examination		X	X	X	X	X	X	X	X	X	X	X	X
Wound photographs	X												
Randomization	X												
Study Drug Wound Injection	X												
Rabies Vaccination	X	X	X	X	X								
Serum RVNA ^a	10 ^a	10 ^b	10 ^b	10 ^b	10 ^b	10	10	10	10	10	10	10	10
Confirmation visit	X	X	X										
Anti-SYN023 serum assay	5 ^a				5 ^b				5				
SYN023 concentration	5 ^a	5 ^b	5 ^b	5 ^b					5				
Adverse events (incl. con. Meds.)	X	X	X	X	X	X							
Solicited adverse events	X	X	X										
Serious adverse events (incl. con. Meds.)	X	X	X	X	X	X	X	X	X	X	X	X	X
Site of injection examination	X	X	X	X	X								
Per visit phlebotomy volume	37	21	15	26	10	18	10	20	10	10	10	10	15
Cumulative phlebotomy volume	37	58	73	99	109	127	137	157	167	177	187	197	212

- a. Study Day 1 samples must be obtained before Study Drug administration
- b. Samples must be obtained before vaccination.
- c. Serum chemistries are total bilirubin, AST, ALT, ALP, creatinine, blood urea nitrogen, sodium, potassium, chloride, bicarbonate, calcium.
- d. Numbers in lab specimen rows indicate **approximate** blood volume in mL. May differ from actual.

